### 11.3 Data Management

The study statistician and staff from the MCC Biostatistics and Bioinformatics Shared Resource Facility will work closely with the study team, the Clinical Research Office, and the Cancer Research Informatics Shared Resource Facility to implement several aspects of data management for this trial. This will include development of eCRFs in the Oncore system, trial-specific processes for data entry, generation of reports, data management and statistical analysis. Specifically, the statistician will attend several meetings including the eCRF development meeting, the data management process meeting and the protocol initiation meeting. Appropriate and accurate collection of primary and secondary study endpoints and inclusion of valid values and range checks for data fields will be designed for the eCRFs. The OnCore clinical trial management system, managed by MCC CRO and Cancer Research Informatics Shared Resource Facility, will be the primary database repository of clinical data from all patients enrolled into this trial. Data will be accessed by the study statistician on a regularly scheduled basis to perform statistical programming for conduct of data quality control, data management, generation of interim reports and statistical analysis. In collaboration with the study team, procedures will be developed for data quality control timelines, resolution of data queries, interim reporting and final data analysis.

A protocol-specific DMP will be authored by a senior data manager in collaboration with the biostatistician and the CRO, each team will be expected to review and sign off on the DMP prior to finalization. In order to maintain best clinical practices in data management, the DMP may include, but is not limited to, CRF/eCRF design, database build and design, database training, edit check/validation specifications, study database testing/release, data and paper workflow, report, metrics, query/discrepancy management, management of external (including lab) data, medical coding, SAE handling/reconciliation, data transfers and database lock. The protocol specific DMP will additionally define the schedule at which data will be accessed by study statisticians to perform statistical programming for conduct of data quality, data control, data management, generation of interim reports and statistical analysis. Cross-team members will collaborate to establish procedures and timelines for quality control, audits, query resolution, interim and final data analysis.

## 12. CORRELATIVE STUDIES

### 12.1 Immune studies:

Two 8.0 ml BD Vacutainer® CPT™ Mononuclear Cell Preparation Tubes - Sodium Citrate will be drawn prior to treatment (on the day of treatment) and 2 weeks after treatment (per study calendar). This should yield up to 16 million PBMCs for each blood draw that will be analyzed by flow cytometry. We will evaluate three different sets of immune cell markers to identify clinical benefit.

#### 12.1.1 Percentage of CD4 T cells and CD8 T cells expressing PD-1 and Ki-67.

- Increased circulating blood levels of Ki-67, PD-1 expressing T cells is a predictor of clinical benefit while on anti-PD-1 therapy. A positive signal will be an increased in cells expressing Ki-67, PD-1 on CD4 and CD8 T cells while on treatment compared to the pre-treatment sample

[47].

12.1.2 Percentage of polyfunctional effector CD4 T cells and CD8 T cells (CD101+ and CD38+) producing IFN $\gamma$  and TNF $\alpha$ .

- Polyfunctional T cells expressing multiple cytokines have been shown to have enhanced anti-tumor activity and CTLA-4 blockade increased the number of polyfunctional T cells in patients with metastatic melanoma. [48]

12.1.3 Percentage of effector CD4 T cells and CD8 T cells expressing CD38, HLA-DR, CD28, ICOS, CD27, and low Bcl2 levels.

- Patients responding to anti-PD-1 therapy have an increase in proliferating effector T cells defined by expression of CD38, HLA-DR, CD28, CD27, ICOS, and low Bcl2 levels.

The part of the study is based on peripheral blood to assess immune activation. The following steps for processing and cryopreservation of blood samples listed below are to be performed in Flow Cytometry and Cell Sorting Shared Resource Facility (FCCS SRF). FCCS provides flow cytometric analysis and cell sorting as well as human immune monitoring services. These services include blood processing and cryopreservation of PBMC. All samples cryopreserved by the FCCS are then banked and managed by the Biospecimen Procurement and Translational Pathology Shared Resource Facility (BPTP SRF) until all samples for a subject have been collected. Once all samples are collected, all stored samples for a subject will be thawed and analyzed simultaneously by the FCCS to obtain correlative endpoints as described above. Data analysis will be performed by [name] with members of his laboratory along with review and discussion of data with Drs. [name] (Co-director FCCS) and [name].

#### Isolation of Mononuclear Cells from Peripheral Blood

- 15 ml of blood will be collected from patients at the indicated times (Whole Blood tube w/ Anticoagulant, BD Vacutainer™ CPT™ Tube with Sodium Citrate). Blood collection will be performed in clinic and handed to FCCS staff.
- The FCIM group will perform the following steps to process the samples for cryopreservation.
  - Centrifuge at 400 x g for 30 minutes at room temperature
  - Aspirate buffy coat at interface, resuspend cells in sterile saline and wash by centrifugation. Repeat wash procedure twice.
  - Resuspend pellet containing PBMCs in ice cold 100% fetal calf serum (FCS)
  - Determine cell concentration and viability
  - Perform flow cytometry analysis on one fresh aliquot and store remainder on ice for cryopreservation by FCCS.

NOTE: PBMCs from all blood collections from each patient will be cryopreserved by the FCCS and banked by the BPTP SRF until all blood collections are completed. Flow cytometric analysis by the FCCS SRF will be performed on fresh samples as they are collected and in bulk on all cryopreserved samples per patient.

- Following determination of cell number and viability, PBMCs in FCS will be adjusted to a

concentration of  $2 \times 10^6$  viable cells/ml.

- $2 \times 10^6$  viable cells will be added to cryopreservation vials containing DMSO to obtain a final concentration of 10% DMSO.
- Vials will be transferred to cryopreservation containers for slow freezing in a  $-80^{\circ}\text{C}$  freezer.
- Following overnight freezing, vials will be transferred to liquid nitrogen freezers maintained by the BPTP SRF for banking until all patient blood samples are collected.

Activation of Peripheral Blood Mononuclear Cell (PBMC) for Intracellular  $\text{IFN}\gamma$  and  $\text{TNF}\alpha$  detection (performed by FCCS SRF).

- Culture  $2 \times 10^6$  freshly thawed PBMC will be incubated for 5 hours in  $37^{\circ}\text{C}$  incubator in complete RPMI medium containing PMA (50ng/ml) and Ionomycin (1ug/mL), plus Brefeldin A to activate cells
- Cells will then be washed by centrifugation and then stained as follows for flow cytometry analysis:
- Suspend cells in FACS buffer (PBS, 1% BSA, sodium azide [0.01%]) at a concentration of  $10^7$  cells per ml
- Add Fc Block to all tubes and incubate for 10 minutes on ice
- Add all of the indicated fluorochrome-labelled antibodies for surface membrane staining as indicated in antibody panels below (**Table**)
  - Anti- human CD3, CD4, CD8 (T cell subset markers)
  - Anti-human CD38, CD101 (effector T cell markers)
  - Anti-human CD27, CD28, Bcl2, HLA-DR, ICOS (activation markers)
  - Anti-human CD279 (PD-1)
- Incubate on ice in the dark for 30 minutes
- Wash cells twice with PBS+Azide to remove excess antibody
- Fix and permeabilize cells (paraformaldehyde/saponin)
- Stain cells for intracellular  $\text{IFN}\gamma$  and  $\text{TNF}\alpha$  with fluorochrome-labeled anti-human  $\text{IFN}\gamma$  and  $\text{TNF}\alpha$  antibodies or Ki-67
- Wash cells by centrifugation and resuspend in FACS buffer for flow cytometry analysis

Flow cytometric analysis (performed by FCCS SRF).

- Set the flow cytometer on the following gates
  - Live cell gate
  - Lymphocyte gate
- Set the following fluorescent gates on the live lymphocyte population
  - CD3+, CD4+ to identify helper T-cells
  - CD3+, CD8+ to identify cytotoxic T-cells
- Analyze both the helper T-cell and cytotoxic T-cell subpopulations for expression of the following
  - Surface expression levels of CD27, CD28, Bcl2, HLA-DR, ICOS, CD38, CD101, and PD-1
  - Intracellular expression levels of IFN $\gamma$  and TNF $\alpha$

| Flow Cytometry Antibody Panels for PD-1/PARP |                                   |
|---|-----------------------------------|
| Panel #1
(Fresh blood)                           | Panel #2
(Cryopreserved blood) |
| CD3   | CD3                               |
| CD4   | CD4                               |
| CD8   | CD8                               |
| PD-1  | CD38                              |
| Ki-67   | CD101                             |
| CD27  | PD-1                              |
| CD28  | IFN gamma                         |
| CD38  | TNF alpha                         |
| Bcl-2   | Viability dye                     |
| HLA-DR  |                                   |
| ICOS  |                                   |
| Viability dye                                       |                                   |

Analysis and storage of flow cytometric data (performed by FCCS SRF).

- Flow cytometric data will be analyzed using FlowJo analytical software to determine the percentage of T cell subsets (CD4+ and CD8+) which express surface and intracellular biomarkers as indicated above.
- Calculated results for each patient and blood collection will be recorded in an Excel spreadsheet. Note: patients will be identified only with the unique code assigned for each patient.

Spreadsheet containing all results will be stored in a private folder on [name] UK server site, which UK backs up daily.

- Raw flow cytometry data and spreadsheet containing calculated results will also be submitted to the OnCore Database, the official database of the MCC CRO, as required.

Only the following individuals will have access to the results in the private folder of [name]: [name], [name], and the biostatistician assigned to the study.

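### Section 12.1 stains and reads Bcl2, an intracellular protein, as a surface marker, so the low-Bcl2 part of exploratory endpoint 12.1.3 may not be validly measured

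*Combined protocol and SAP*

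**What the plan says.** Endpoint 12.1.3, which repeats objective 1.3.1.3, is the "Percentage of effector CD4 T cells and CD8 T cells expressing CD38, HLA-DR, CD28, ICOS, CD27, and low Bcl2 levels".

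Only one staining sequence is written in Section 12.1. It opens with the instruction "Add all of the indicated fluorochrome-labelled antibodies for surface membrane staining as indicated in antibody panels below". One line of the antibody list under that instruction reads "Anti-human CD27, CD28, Bcl2, HLA-DR, ICOS (activation markers". The cells are then incubated, washed twice, and taken to the next step, "Fix and permeabilize cells (paraformaldehyde/saponin". The stain after that step names IFN-gamma and TNF-alpha "antibodies or Ki-67"; Bcl2 is not named there.

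The flow cytometric analysis list has two read-out lines. The first is "Surface expression levels of CD27, CD28, Bcl2, HLA-DR, ICOS, CD38, CD101, and PD-1". The second gives the intracellular read-outs as IFN-gamma and TNF-alpha only.

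In the panel table, Bcl-2 and Ki-67 appear only in Panel #1 (fresh blood). IFN-gamma and TNF-alpha appear only in Panel #2 (cryopreserved blood).

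**The concern.** Bcl2 is an intracellular protein. This is basic cell biology rather than a statement in the documents. An antibody applied to intact cells and washed away before permeabilisation has little access to it, so a cell with much Bcl2 and a cell with little may give similar, weak signals.

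For most markers a failed stain shows up as an unexpectedly low positive count. Here the endpoint asks for low Bcl2, so the failure is silent: weak signal is exactly what the phenotype requires. Cells that should be excluded for high Bcl2 would tend to be kept, and the baseline-to-treatment comparison of Bcl2 would carry little information about the drugs.

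**Working it through.** The documents state no figure for Bcl2, so there is nothing to reproduce. The check sets the panel table, the staining order and the read-out lists of Section 12.1 side by side.

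| Marker | Panel | Stained | Read out as |
|---|---|---|---|
| CD27, CD28, HLA-DR, ICOS | #1 only | before permeabilisation | surface |
| Bcl2 | #1 only | before permeabilisation | surface |
| CD38, PD-1 | #1 and #2 | before permeabilisation | surface |
| CD101 | #2 only | before permeabilisation | surface |
| Ki-67 | #1 only | after permeabilisation | not listed |
| IFN-gamma, TNF-alpha | #2 only | after permeabilisation | intracellular |

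1. *Is the Bcl2 placement a slip in one line?* No. The staining list and the read-out list agree in treating it as a surface marker.

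2. *Does the written sequence apply to the tube that contains Bcl2?* Its heading concerns cytokine detection, and it starts from cells described as "freshly thawed PBMC will be incubated for 5 hours in" the incubator. That matches Panel #2, which has no Bcl-2. But the antibody list includes CD27, CD28, Bcl2, HLA-DR and ICOS, and the later stain offers Ki-67. All six are in Panel #1 only, so the sequence covers both panels despite its heading. For the fresh cells the text otherwise says only "Perform flow cytometry analysis on one fresh aliquot and store remainder on ice for cryopreservation by FCCS"; no separate staining order is given.

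3. *Does permeabilising Panel #1 cells for Ki-67 rescue Bcl2?* No. The anti-Bcl2 has already been added and washed off by then.

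4. *How much of the endpoint is affected?* The phenotype has six markers: CD38, HLA-DR, CD28, ICOS, CD27 and Bcl2. Five are stained and read as surface markers, with no conflict in the text, so 6 − 5 = 1 component is in question. The full composite requires all six and inherits the problem.

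5. *Which direction, and how large?* Let L be the true share of otherwise qualifying cells that are low for Bcl2, and R the share that reads low. The composite count is inflated by the factor R / L. If the antibody mostly misses its target, R tends to exceed L, so the direction is over-counting. The documents give neither L nor R. Even under the extreme assumption R = 1, an assumed L of 90% gives 1 / 0.9 ≈ 1.1, and an assumed L of 10% gives 1 / 0.1 = 10. That range is too wide to support any single figure. There is also no stated cut-off for low Bcl2: the analytical procedures record percent positive and mean fluorescence intensity per marker and leave population finding to the SPADE algorithm.

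**The case against.** The strongest reply is that the written steps belong to the thawed-cell cytokine assay, whose panel contains no Bcl-2, and that a specialised flow cytometry facility will stain an intracellular protein correctly whatever a bullet list says. The first half fails on the text: the list is full of markers found only in Panel #1. If it were accepted, Panel #1 would have no staining order at all, which needs the same repair. The second half may well be true. If so, only the wording is wrong, but the protocol gives the reader no means of knowing it.

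A second reply is that the matter is small, and this stands. The immune markers are exploratory and described as preliminary. Section 11.2 names PD-1, Ki-67, CD101 and CD38, not Bcl2. Its list is introduced as inclusive rather than complete, so Bcl2 is not ruled out of the paired comparisons, but no decision depends on it.

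Three stronger readings are tempting, and the documents do not support them:

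- A reader might infer that practically all T cells will read low, with no change in any of the 36 planned patients. No figure supports this. It assumes literal execution, a particular cut-off and complete sample pairs.
- A reader might infer that endpoint 12.1.3 cannot be derived at all. Five of its six markers are unaffected.
- A reader might infer that endpoint 12.1.1 is also lost, because Ki-67 is missing from the intracellular read-out line. But Ki-67 is in Panel #1, is stained after permeabilisation, and is named for summary and paired comparison in Section 11.2. This is an omission from one line.

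**Conclusion.** The point holds as a minor procedural error. Followed as written, Section 12.1 stains and reads Bcl2 in a way that is unlikely to measure it. The low-Bcl2 component of exploratory endpoint 12.1.3, and so the full composite phenotype, may not be valid and would tend to be over-counted by an amount that cannot be calculated from the documents. The primary PFS analysis and the sample size are untouched.

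The conclusion rests on two assumptions: that Bcl2 is intracellular, which is textbook knowledge, and that the laboratory works to the written order. If the laboratory already stains Bcl2 after permeabilisation, the data are sound in this respect and only the text needs correcting.

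**What to change.** For Panel #1 (fresh blood), move anti-Bcl2 out of the surface-stain list and into the post-permeabilisation stain alongside Ki-67. Delete Bcl2 from the surface read-out line. Replace the single intracellular line with read-outs by panel: Ki-67 and Bcl2 for Panel #1, IFN-gamma and TNF-alpha for Panel #2. It would be sensible to state at the same time how low Bcl2 is to be gated.

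The cost is small: an edit to the protocol or laboratory manual, using a permeabilisation step that is already performed. The laboratory should confirm that its Bcl2 antibody works with that fixation and permeabilisation step, because the documents give no antibody clone or validation detail. The correction is worth making promptly, because Panel #1 is run on fresh aliquots as they are collected and a wrongly stained one cannot be repeated fresh.

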#### Analytical procedures

Patient PBMCs will be analyzed by the FCCS SRF for the percentage of cells expressing each marker and for the mean fluorescence intensity for each marker. PBMC samples will be analyzed on a Beckman-Coulter CytoFLEX LX cell analyzer with 19 color detection capacity. Flow cytometric data sets will be interpreted by the MCC Biostatistics and Bioinformatics Shared Resource Facility by computational flow cytometry using SPADE algorithm to automatically identify populations.

12.1.4 Assessment of baseline tumor mutational burden and correlation with radiological response.

All patients enrolled in the study will be assessed as to whether they have also enrolled on the Markey Cancer Center Total Cancer Care (ORIEN protocol; Yes/No status will be documented in the eCRF).

- Patients enrolled on ORIEN protocol undergo whole exome sequencing of tumor tissue (at baseline, and progression, when available) and germline mutation testing via peripheral blood or buccal swab. Genomic profiling will be done under Markey Cancer Center Total Cancer Care (ORIEN) protocol, wherein all consenting patients treated at MCC are sequenced. Genomic testing is funded by the ORIEN protocol.

For our on-study patients who are also co-enrolled in ORIEN (participant status is "Yes"), we will study patterns of tumor mutation burden and correlate genomic data to durability of treatment response and treatment resistance patterns using bioinformatics pipelines developed by the Biostatistics and Bioinformatics Shared Resource Facility at Markey.

12.1.5 The ORIEN Total Cancer Care is a very large clinical research protocol and data are stored within the Moffitt Data Warehouse (DW). For further details, please visit [www.oriencancer.org](http://www.oriencancer.org).

## APPENDIX A. ECOG PERFORMANCE STATUS CRITERIA

| ECOG Performance Status Scale |  |
|--------------------------------------|--|
| Grade                         | Descriptions  |
| 0                                    | Normal activity. Fully active, able to carry on all pre-disease performance without restriction.   |
| 1                                    | Symptoms, but ambulatory. Restricted in physically strenuous activity, but ambulatory and able to carry out work of a light or sedentary nature ( e.g. , light housework, office work). |
| 2                                    | In bed <50% of the time. Ambulatory and capable of all self-care, but unable to carry out any work activities. Up and about more than 50% of waking hours.                                     |
| 3                                    | In bed >50% of the time. Capable of only limited self-care, confined to bed or chair more than 50% of waking hours.  |
| 4                                    | 100% bedridden. Completely disabled. Cannot carry out any self-care. Totally confined to bed or chair.   |
| 5                                    | Dead.  |

## **APPENDIX B. ADVERSE EVENTS LIST FOR RUCAPARIB**

### **Rucaparib Side Effects**

The following is a list of reported side effects as well as other notable side effects considered to be possibly due to rucaparib, as reported by physicians about their patients who are taking rucaparib alone:

#### **Very common (Occurring in 10% or more of patients)**

- Nausea
- Feeling tired
- Low Blood Counts (red blood cells, white blood cells, and platelets). Sometimes fever occurs with the low blood counts. These low blood count effects may be more likely to occur after multiple cycles of treatment.
  - A low red blood cell count may make you feel tired or dizzy. If you feel dizzy while taking rucaparib, you should avoid potentially hazardous tasks such as driving or operating machinery.
  - A low white blood cell count puts you at higher risk for bacterial or viral infection. Having a high temperature or fever while your white blood cell count is low is a medical emergency and you must proceed to the nearest emergency room as soon as possible
  - A low platelet count affects the ability of your blood to clot and could lead to bleeding events. Symptoms include but are not limited to easy bruising, prolonged bleeding from cuts, blood in stools or urine, or nose bleeding. It is possible that rucaparib may make your skin and eyes more sensitive to sunlight. You should take all of the usual sun protection precautions when going outside. It is advised that you avoid excessive sun exposure, wear protective clothing (including wearing a hat and sunglasses), and use sunscreen regularly (sun protection factor 50 or greater).
- A low phosphate level in your blood. Usually there are no symptoms but if the levels are critically low, you may notice trouble breathing, confusion, muscle weakness, or irritability.
- Increase in cholesterol. If your cholesterol increases significantly, your doctor may prescribe a medicine to lower your cholesterol level.
- Changes in kidney and liver function blood tests. These changes will be evaluated by your study doctor along with any other side effects that you are experiencing as well as other test results.
- Changes in your sense of taste.
- Stomach-related effects such as constipation, vomiting, diarrhea, decreased appetite, stomach pain (epigastric pain), and indigestion.
- Difficulty breathing
- Dizziness
- Photosensitivity reaction
- Fever sometimes can occur independent of a low blood count. If you experience elevation of your temperature, please refer to your study doctor for fever management.
- Difficulty sleeping

### **Common Side Effects of Rucaparib (Occurring in 1% to less than 10% of patients)**

- Rash, which will appear as changes in your skin color (e.g. redness) and texture (e.g. bumps, blisters, peeling). Some rashes may be itchy, painful, or cause no symptoms at all. This can vary in severity from mild to severe.
- Upper airway infection (like the common cold). You may experience infections involving the nose, pharynx, larynx, and sinuses. Symptoms include a blocked (congested nose, a runny nose, and sneezing. You may also have clear discharge (mucus) from the nose. You may feel generally unwell and may also be associated with fever. Treatment is usually supportive but if symptoms persist please inform your doctor.
- Hand-Foot Syndrome (Palmar-plantar erythrodysesthesia syndrome) When a small amount of drug leaks out of the blood vessels, it damages the surrounding tissues. Symptoms would include tingling, burning, redness, flaking, swelling, blistering, and sores of the hands and feet due to the increased friction and heat your extremities are exposed to. If you experience these symptoms, apply ice packs and elevate hands and feet, then contact your study doctor immediately for treatment.

